Once candidate auto-antigens have been identified in the selected group of patients with severe eosinophilic asthma and EGPA we will then examine their prevalence in serum samples from a wider selection of patients with eosinophilic airways diseases including mild-to-moderate asthma, severe eosinophilic asthma, EGPA, nasal polyposis and eosinophilic COPD as well as healthy controls. Length of disease, atopy, presence/absence nasal polyps, gender, age will be examined as co-variates. Correlations with highest blood eosinophil counts, requirement for oral corticosteroids and presence of other auto-antibodies, e.g. anti-MPO ANCA, will be examined. In particular we will look for the presence of novel autoantibodies in specific patient subsets: i) ANCA negative, ii) ANCA positive by immunofluorescence but negative for anti-MPO and anti-PR3 antibodies, iii) ANA positive but ANCA and ENA negative; since patients in all three groups may have novel, as yet undetermined autoantibodies. ROC AUC analyses will be conducted to ascertain the predictive value of blood auto-antibodies for diagnosis of eosinophilic airways disease.

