6.1. Study Outcomes / Endpoints

Primary objectives

- The presence of serum and/or sputum auto-antibodies to eosinophil and/or basement membrane proteins will be established in severe eosinophilic asthma and EGPA cohorts, and patients with other asthma phenotypes and related eosinophilic diseases.
- Whether auto-antibodies to post-translationally modified self-antigens are more prevalent than to native self-antigens will be examined, and which post-translational

modifications are important to be studied (including particulate matter air pollution as a potential combined stimulus of eosinophil activation and protein modification).

Primary outcomes

- Correlations of auto-antibodies to clinical variables such as spirometry (FEV1 % predicted), pattern of organ involvement, age of onset, requirement for maintenance of oral corticosteroids, eosinophil count, highest recorded eosinophil count and FeNO will be studied.
- Predictive ability to diagnose severe eosinophilic asthma / EGPA of relevant auto-antibodies will be examined by ROC AUC analysis.

Secondary outcomes

- Exploratory Outcomes: Further experimental assays may be conducted to examine immunological mechanisms underpinning associations of auto-antibodies to disease.

7. Study population

90 patients under the care of the Barts Health NHS Trust and Royal Free London NHS Trust with severe eosinophilic asthma, EGPA, eosinophilic COPD and other related pathologies will be recruited.

At least 60 patients will have severe eosinophilic asthma and/or EGPA, and will be recruited from the regional North Central and East London Severe Asthma Service, the Royal Free London NHS Trust and from the Barts Arthritis Centre, with multi-disciplinary consensus diagnoses of severe eosinophilic asthma and/or EGPA respectively. Patients will be phenotyped with blood leucocyte differential, lung function tests and FeNO as appropriate in conjunction with detailed medical history.

Up to a further 30 patients with milder asthma, other vasculitides, eosinophilic COPD, and/or eosinophilic oesophagitis will be recruited from other clinics at Barts Health NHS Trust and the Royal Free London NHS Trust.

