7.1. Inclusion criteria

- *Informed consent*
- *Age 18 years and over*
- *Patients:*
 - *Severe Eosinophilic Asthma*
(*with multi-disciplinary diagnosis as per ERS/ATS Criteria, blood eosinophils $\geq 0.3 \times 10^9/L$ on inhaled corticosteroids*); or
 - EGPA*
(*as per American College of Rheumatology (ACR) Criteria*); or
 - Eosinophilic COPD*
(*post-bronchodilator FEV1/FVC $< 70\%$ predicted, absence of bronchodilator reversibility, > 20 pack year smoking history, no medical history of current asthma, blood eosinophils $\geq 0.3 \times 10^9/L$*); or
 - Eosinophilic oesophagitis*
(*with diagnostic histology*); or
 - Granulomatosis with Polyangiitis (GPA, formerly called Wegener's)*
(*as per American College of Rheumatology (ACR) Criteria*)
- *Healthy Controls:*
 - *No acute medical illness.*
 - *No diagnosed chronic respiratory disease, allergy or infective condition, including no history of asthma.*
 - *No history of EGPA or other vasculitis,*
 - *No systemic immunosuppressive medication.*

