7.2. Exclusion criteria

- *Any inclusion criteria not met*
- *Known Pregnancy*
- *Anaemia*
- *Donation of more than 240mls blood in the last sixteen weeks (four months) to any other research study or as a donation to the National Blood Transfusion Service*
- *Rituximab, plasmapharesis or polyclonal immunoglobulin infusion (ever)*

8. Study design

Study Visit (Patients)

This is a single study visit encompassing patient recruitment, consent, data collection and provision of a peripheral blood sample with/without concurrent sputum sample, with no follow-up visits.

Patients will be recruited via Outpatient Clinics conducted at St Bartholomew's (Bart's) Hospital, The Royal London Hospital, and Mile End Hospital (all Bart's Health NHS Trust), Royal Free London NHS Trust, as well as from inpatients at these hospitals under the care of the Respiratory Medicine and Rheumatology teams (including those under other services needing inpatient respiratory medicine or rheumatology review).

Potential patients will be identified by their clinical team and invited to participate. If interested they will be given a Participant Information Sheet (PIS). Informed Consent and Screening will be undertaken by a GCP-trained member of the clinical team or GCP-trained researcher. An anonymised data collection case report form (CRF) will be completed by a member of the clinical team and a linked (anonymised) blood sample collected by a staff member trained in phlebotomy. If the patient is able to spontaneously produce sputum, and there is no clinical concern about TB infection, then they will be asked to cough a sample in to a sterile sample pot.

The linked anonymised CRF and samples will then be taken to the research laboratories at QMUL for immune cell analysis. Laboratory immunology studies will be conducted by as per protocol (Section 14) by a dedicated Post-Doctoral Research Assistant.

Study Visit (Healthy Controls)

There is a single study visit encompassing healthy control recruitment, consent, data collection and taking of blood sample, with no follow-up visits.

Healthy controls will be recruited at QMUL, Bart's Health and Royal Free sites via poster advertisement.

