Healthy controls will be identified by the research team and invited to participate. If interested they will be given a Participant Information Sheet (PIS). Informed Consent and Screening will be undertaken by a GCP-trained researcher. A limited anonymised data collection case report form (CRF) will be completed by a member of the research team and a linked (anonymised) blood sample collected by a staff member trained in phlebotomy. The linked anonymised CRF and blood sample will then be transferred to the research laboratories at QMUL for immune cell analysis.

[figure not shown]

Figure 1: Study design graphic

9. Study procedures

Invitation to Participate:

Invitation to Participate will be by members of their clinical team for Patients and by members of the research team for Healthy Controls. Before participants are invited to participate, capacity to process samples from that type of participant will be discussed with the research team. Invited participants will be given a copy of the Participant Information Sheet (PIS) at invitation to participate.

Informed Consent Procedures and Screening:

Potential participants interested in the study will be given time to read the PIS and ask questions from a GCP-trained member of the research team who may or may not be a member of the clinical team treating the participant. After questions have been answered, potential participants will be asked to complete the written informed Consent Form. Consenting participants will then be briefly screened to check they fulfil inclusion/exclusion criteria.

Data Collection (CRF):

A member of the clinical team (for patient participants) and the research team (for healthy control participants) will complete the case report form (CRF) which contains only pseudoanonymised information but with a study code to link the patient to the samples (and to Consent Form for governance purposes).

Sample Collection:

A peripheral blood sample (up to 50ml total volume) will be collected using aseptic technique into vacutainers or anti-coagulated syringe by staff trained in phlebotomy techniques and securely transported to the research laboratories for analysis.

If the patient is able to spontaneously produce sputum, and there is no clinical concern about TB infection, then they will be asked to cough a sample in to a sterile sample pot.

Samples will be analysed as per Section 14.

Subject Withdrawal:

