13.2. Source data

Case Report Form (Patients) data variable list:

1. Age
2. Gender
3. Ethnicity (optional)
4. Occupational history
5. Confirmation participant meets Inclusion and Exclusion criteria (Yes/No)
6. Smoking history
7. Diagnosed medical condition(s) and basis for diagnoses with focus on diagnostic criteria for Severe Eosinophilic Asthma, EGPA
8. Suspected medical conditions(s)
9. Immunosuppressive medication(s) dose regimes and history
10. Previous treatment history, especially corticosteroid history
11. Full blood count (haematology)
12. Most recent and previous FeNO breath tests, if done
13. Auto-immune serology results
14. Spirometry and gas transfer tests, if done
15. Highest previous blood eosinophil count, ANCA serology (immunofluorescence, anti-PR3 and anti-MPO antibody titre) and trend
16. Investigations for target organ involvement in patients with suspected vasculitis including histology
17. Clinical disease activity measures (for example Birmingham Vasculitis Activity Score (BVAS), Asthma Control Questionnaire (ACQ)-6)

Case Report Form (Healthy Control) data variable list:

1. Age
2. Gender
3. Ethnicity (optional)
4. Occupational history
5. Confirmation participant meets Inclusion and Exclusion criteria (Yes/No)
6. Smoking history

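### Section 7 plans to recruit milder asthma and the first primary objective covers other asthma phenotypes, but Section 7.1 admits asthma only as severe eosinophilic asthma

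*Combined protocol and SAP*

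**What the plan says.** Three statements in the protocol look beyond severe eosinophilic asthma.

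- **Section 7, Study population:** "Up to a further 30 patients with milder asthma, other vasculitides, eosinophilic COPD, and/or eosinophilic oesophagitis will be recruited from other clinics". These places come on top of at least 60 patients with severe eosinophilic asthma and/or EGPA, within a total of 90 patients.
- **Section 6, Study objectives:** once candidate auto-antigens are found, their prevalence is to be examined in a wider set of patients, "including mild-to-moderate asthma, severe eosinophilic asthma, EGPA, nasal polyposis and eosinophilic COPD as well as healthy controls".
- **Section 6.1, first primary objective:** the presence of auto-antibodies is to be established in "severe eosinophilic asthma and EGPA cohorts, and patients with other asthma phenotypes and related eosinophilic diseases". The protocol does not define which other phenotypes are meant.

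The eligibility text is narrower. Section 7.1 lists five alternative patient diagnoses: severe eosinophilic asthma, EGPA, eosinophilic COPD, eosinophilic oesophagitis and GPA. The COPD entry requires "no medical history of current asthma". Healthy controls must have "No diagnosed chronic respiratory disease, allergy or infective condition, including no history of asthma". Section 7.2 then excludes on "Any inclusion criteria not met".

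The list is applied to each participant. Section 9 says "Consenting participants will then be briefly screened to check they fulfil inclusion/exclusion criteria", and Section 13.2 puts the confirmation on the case report form as a yes/no item for patients and for controls.

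**The concern.** A recruiting clinician who reads Section 7 would approach patients with milder asthma. The same clinician, at screening, would find no criterion under which to enrol them and an exclusion that rules them out.

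The group matters to the plan's own aims: it is named in the recruitment plan, in the prevalence stage and, in more general words, in a primary objective. If the eligibility list is obeyed, the study closes with no patient enrolled because of non-severe asthma, and it cannot report on that part of what it set out to establish. If the recruitment plan is obeyed instead, each such enrolment departs from 7.1 and 7.2 and would have to be recorded as failing the criteria.

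**Working it through.** The point rests on text and not on a power or sample-size figure. Section 10.1 gives no power calculation, so there is no planned figure to reproduce.

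**Step 1: head-count.** At least 60 + up to 30 = 90 patients (Section 7); 90 + 30 controls = 120 (synopsis). The numbers agree, so the conflict concerns who may enter and not how many.

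**Step 2: each route into the study, tested against a person whose only relevant diagnosis is milder or other non-severe-eosinophilic asthma.**

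| Entry in Section 7.1 | Admits this person? | Reason |
|---|---|---|
| Severe eosinophilic asthma | No | Requires the severe diagnosis by a multi-disciplinary team, plus an eosinophil threshold |
| EGPA | No | Requires EGPA |
| Eosinophilic COPD | No | Current asthma is barred |
| Eosinophilic oesophagitis | No | Requires diagnostic histology of that disease |
| GPA | No | Requires GPA |
| Healthy control | No | Any history of asthma is barred |

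Patient entries that admit the person: 0 of 5. The control route is closed as well.

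**Step 3: is the list binding?** Yes. Section 7.2 turns failure to meet 7.1 into an exclusion, and Sections 9 and 13.2 have it checked and recorded.

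**Step 4: does another passage supply the entry?**

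- The synopsis names four diagnoses (the 7.1 list without GPA), and milder asthma is not among them.
- Section 7 opens with a general phrase about related conditions. It describes the population and is not a criterion.
- The only other sample source described in Section 7 is a future replication set. It is limited to severe eosinophilic asthma and is to be collected under a separate ethics application.

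**Step 5: which parts of the plan are touched?**

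| Part of the plan | Affected? |
|---|---|
| First primary objective: severe eosinophilic asthma, EGPA, related eosinophilic diseases | No; 7.1 has entries for these |
| First primary objective: other asthma phenotypes | Yes |
| Section 6 prevalence stage: mild-to-moderate asthma | Yes |
| Second primary objective (modified versus native antigens) | No |
| Synopsis aim (severe eosinophilic asthma and EGPA) | No |
| Cohort of at least 60; 30 controls | No |

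**The case against.** The strongest reply is that nothing is strictly breached. Section 7 sets a ceiling and joins its groups with and/or, so a site that enrols no milder asthma complies with Sections 7, 7.1 and 7.2 together. This is also a single-visit exploratory pilot, sized by experience and feasibility, and no test or threshold depends on a milder-asthma group. Screening would expose the mismatch at the first such patient. All of this is correct, and it limits the weight of the point. It does not remove it: compliance by enrolling nobody leaves the wider-asthma part of the first primary objective and of the prevalence stage without participants. Pilot status does not explain why the eligibility list shuts out a group that the plan names for recruitment.

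A reader might also infer more than the documents support, in four ways.

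- **That the ROC analysis is compromised**, because severe disease could not be told apart from asthma in general. No ROC comparator is named, and the target is worded differently in Sections 6, 6.1 and 10.2. Under the Section 6 wording, mild-to-moderate asthma would be among the cases; under Section 6.1 it lies outside the target. The protocol states no test of severe against milder asthma. An added entry alone would not settle any of this, because the ceiling would still allow zero such patients.
- **That nasal polyposis and other vasculitides are equal contradictions.** Nasal polyposis is named as a disease group only in Section 6, where polyps are also a co-variate, and such patients can enter through another listed diagnosis. GPA can be read as what Section 7 means by other vasculitides. Each has a reading without conflict.
- **That a minimum number of milder-asthma patients is required.** Nothing in the documents calls for one; it would be a design preference.
- **That no person with milder asthma can take part at all.** The EGPA, eosinophilic oesophagitis and GPA entries are silent on asthma, so a patient with one of those diagnoses and milder asthma can enter. What is missing is entry on asthma alone.

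**Conclusion.** The contradiction is real and should be corrected. Sections 6, 6.1 and 7 name milder, mild-to-moderate or other asthma; 0 of the 5 patient entries in 7.1 admit it on its own; and 7.2 makes that list binding.

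The consequence is confined to one part of the first primary objective and one part of the Section 6 prevalence stage. No effect on an estimate can be calculated, because the protocol gives no number per disease. The only bound is the Section 7 ceiling of 30 of 90 patients (30/90 = 33%), shared among four named groups. That is a ceiling on places and not a measure of harm.

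The conclusion assumes that 7.1 is the complete eligibility list. This is supported by the unbroken chain of alternatives ending at GPA and by the absence of milder asthma from the synopsis. It also takes the undefined phrase about other phenotypes to mean asthma that is not severe eosinophilic asthma, which is its plain sense beside the cohorts named in the same sentence.

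**What to change.** Reconcile Sections 6, 6.1, 7, 7.1 and the synopsis in one of two ways.

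1. **Add an entry.** Put into 7.1 and the synopsis an entry for milder asthma, and for any other asthma phenotypes that are intended, within the existing up-to-30 places. The sponsor should supply the clinical definition. This matches the recruitment intent in Section 7. It keeps the first primary objective only for the phenotypes actually added, and fewer places may go to the other listed diseases.
2. **Remove the group.** Delete milder and mild-to-moderate asthma from Sections 6 and 7, and the reference to other asthma phenotypes from the first primary objective. The wider-asthma part of that objective is then given up.

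Either way the cost is one protocol and ethics amendment, with no increase in the 120 participants. In the same amendment the sponsor may confirm whether nasal polyposis as a sole diagnosis, or vasculitides other than EGPA and GPA, are meant to be eligible.

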7.1. Inclusion criteria

- *Informed consent*
- *Age 18 years and over*
- *Patients:*
 - *Severe Eosinophilic Asthma*
(*with multi-disciplinary diagnosis as per ERS/ATS Criteria, blood eosinophils $\geq 0.3 \times 10^9/L$ on inhaled corticosteroids*); or
 - EGPA*
(*as per American College of Rheumatology (ACR) Criteria*); or
 - Eosinophilic COPD*
(*post-bronchodilator FEV1/FVC $< 70\%$ predicted, absence of bronchodilator reversibility, > 20 pack year smoking history, no medical history of current asthma, blood eosinophils $\geq 0.3 \times 10^9/L$*); or
 - Eosinophilic oesophagitis*
(*with diagnostic histology*); or
 - Granulomatosis with Polyangiitis (GPA, formerly called Wegener's)*
(*as per American College of Rheumatology (ACR) Criteria*)
- *Healthy Controls:*
 - *No acute medical illness.*
 - *No diagnosed chronic respiratory disease, allergy or infective condition, including no history of asthma.*
 - *No history of EGPA or other vasculitis,*
 - *No systemic immunosuppressive medication.*

7.2. Exclusion criteria

- *Any inclusion criteria not met*
- *Known Pregnancy*
- *Anaemia*
- *Donation of more than 240mls blood in the last sixteen weeks (four months) to any other research study or as a donation to the National Blood Transfusion Service*
- *Rituximab, plasmapharesis or polyclonal immunoglobulin infusion (ever)*

8. Study design

Study Visit (Patients)

This is a single study visit encompassing patient recruitment, consent, data collection and provision of a peripheral blood sample with/without concurrent sputum sample, with no follow-up visits.

Patients will be recruited via Outpatient Clinics conducted at St Bartholomew's (Bart's) Hospital, The Royal London Hospital, and Mile End Hospital (all Bart's Health NHS Trust), Royal Free London NHS Trust, as well as from inpatients at these hospitals under the care of the Respiratory Medicine and Rheumatology teams (including those under other services needing inpatient respiratory medicine or rheumatology review).

Potential patients will be identified by their clinical team and invited to participate. If interested they will be given a Participant Information Sheet (PIS). Informed Consent and Screening will be undertaken by a GCP-trained member of the clinical team or GCP-trained researcher. An anonymised data collection case report form (CRF) will be completed by a member of the clinical team and a linked (anonymised) blood sample collected by a staff member trained in phlebotomy. If the patient is able to spontaneously produce sputum, and there is no clinical concern about TB infection, then they will be asked to cough a sample in to a sterile sample pot.

The linked anonymised CRF and samples will then be taken to the research laboratories at QMUL for immune cell analysis. Laboratory immunology studies will be conducted by as per protocol (Section 14) by a dedicated Post-Doctoral Research Assistant.

Study Visit (Healthy Controls)

There is a single study visit encompassing healthy control recruitment, consent, data collection and taking of blood sample, with no follow-up visits.

Healthy controls will be recruited at QMUL, Bart's Health and Royal Free sites via poster advertisement.

Healthy controls will be identified by the research team and invited to participate. If interested they will be given a Participant Information Sheet (PIS). Informed Consent and Screening will be undertaken by a GCP-trained researcher. A limited anonymised data collection case report form (CRF) will be completed by a member of the research team and a linked (anonymised) blood sample collected by a staff member trained in phlebotomy. The linked anonymised CRF and blood sample will then be transferred to the research laboratories at QMUL for immune cell analysis.

[figure not shown]

Figure 1: Study design graphic

9. Study procedures

Invitation to Participate:

Invitation to Participate will be by members of their clinical team for Patients and by members of the research team for Healthy Controls. Before participants are invited to participate, capacity to process samples from that type of participant will be discussed with the research team. Invited participants will be given a copy of the Participant Information Sheet (PIS) at invitation to participate.

Informed Consent Procedures and Screening:

Potential participants interested in the study will be given time to read the PIS and ask questions from a GCP-trained member of the research team who may or may not be a member of the clinical team treating the participant. After questions have been answered, potential participants will be asked to complete the written informed Consent Form. Consenting participants will then be briefly screened to check they fulfil inclusion/exclusion criteria.

Data Collection (CRF):

A member of the clinical team (for patient participants) and the research team (for healthy control participants) will complete the case report form (CRF) which contains only pseudoanonymised information but with a study code to link the patient to the samples (and to Consent Form for governance purposes).

Sample Collection:

A peripheral blood sample (up to 50ml total volume) will be collected using aseptic technique into vacutainers or anti-coagulated syringe by staff trained in phlebotomy techniques and securely transported to the research laboratories for analysis.

If the patient is able to spontaneously produce sputum, and there is no clinical concern about TB infection, then they will be asked to cough a sample in to a sterile sample pot.

Samples will be analysed as per Section 14.

Subject Withdrawal:

In the event that a participant asks to withdraw from the study before the end of the Study Visit then the CRF and samples will be securely destroyed and no recording / analysis of data from that patient undertaken. In the event a participant asks to withdraw from the study after the first Study Visit has been completed the research team will be asked to withdraw any unreported linked data from that participant from the study.

Recruitment Time-Frame

Recruitment will be completed within 21 months. Laboratory analysis of collected samples will continue up to 30 months. Residual samples may be stored for future ethically approved studies.

End of Study Definition

The end of the study is at completion of laboratory sample analysis for the last participant recruited. Statistical analysis of data may continue after the End of Study.

10. Statistical considerations

